19. ADMINISTRATIVE CONSIDERATIONS

19.1. Investigators

The investigator must agree to the responsibilities and obligations listed below, as specified by the appropriate FDA regulatory requirements or ICH/GCP guidelines:

- Agree to conduct the study in accordance with the relevant current protocol
- Agree to personally conduct or supervise the described investigation(s)
- Agree to inform any patients, or persons used as controls, that the IMP are being used for investigational purposes and ensure that the requirements relating to obtaining informed consent and IRB review and approval are met
- Agree to report adverse experiences that occur during the course of the investigation(s)
- Read and understand the information in the IB, including the potential risks and side effects of the IMP
- Ensure that all associates, colleagues, and employees assisting in the conduct of the study are informed about their obligations in meeting the above commitments
- Maintain adequate and accurate records and make those records available for inspection
- Ensure that an appropriate IRB will be responsible for the initial and continuing review and approval of the clinical investigation
- Agree to promptly report to the IRB all changes in the research activity and all unanticipated problems involving risks to patients or others
- Agree to not make changes in the research without IRB approval, except where necessary to eliminate apparent hazards to patients
- Comply with all other requirements regarding the obligations of clinical investigators and all other pertinent requirements.
- Refer also to:
 - FDA Regulations Related to GCP and Clinical Trials: http://www.fda.gov/oc/gcp/regulations.html
 - Guidance and Information Sheets on GCP in FDA-Regulated Clinical Trials: http://www.fda.gov/oc/gcp/guidance.html
 - Guidance for IRBs and Clinical Investigators: http://www.fda.gov/oc/ohrt/irbs/default.htm
 - Guidance for Industry E6 Good Clinical Practice: Consolidated Guidance: http://www.fda.gov/cder/guidance/959fnl.pdf

19.3. Amendments and Study Termination

Changes to the research covered by this protocol must be implemented by formal protocol amendment. All amendments to the protocol must be initiated by the Sponsor and signed and dated by the investigator. Protocol amendments must not be implemented without prior IRB approval. Documentation of amendment approval by the investigator and IRB must be provided to the Sponsor or its authorized representative. When the change(s) involve only logistic or administrative aspects of the study, the IRB only needs to be notified.

During the course of the study, in situations where a departure from the protocol is unavoidable, the investigator will contact the Medical Monitor. Except in emergency situations, this contact should be made before implementing any departure from the protocol. In all cases, contact with the Medical Monitor must be made as soon as possible to discuss the situation and agree on an appropriate course of action. The data recorded on the eCRF and source documents will reflect

any departure from the protocol and the source documents will describe the departure and the circumstances requiring it.

The Sponsor reserves the right to terminate this study at any time.

19.4. Financial Disclosure

Prior to the start of the study, investigators will release sufficient and accurate financial information that permits the Sponsor to demonstrate that an investigator and all study relevant assigned personnel have no personal or professional financial incentive regarding the future approval or disapproval of the IMP such that his or her research might be biased by such incentive.

20. PUBLICATION AND DISCLOSURE POLICY

It is understood by the investigator that the information and data included in this protocol may be disclosed to and used by the investigator's staff and associates as may be necessary to conduct this clinical study.

All information derived from this clinical study will be used by the Sponsor (or designee) and therefore, may be disclosed by the Sponsor (or designee) as required to other clinical investigators, to the FDA, European Medicines Agency, and to other government agencies, or in connection with intellectual property filings or publications. In order to allow for the use of the information derived from this clinical study, it is understood by the investigator that there is an obligation to provide the Sponsor with complete test results and all data from this clinical study. The investigator agrees to maintain this information in confidence, to use the information only to conduct the study, and to use the information for no other purpose without the Sponsor's prior written consent (or as otherwise may be permitted pursuant to a written agreement with the Sponsor or its designee).

The results of the study will be reported in a clinical study report prepared by the Sponsor (or designee), which will contain eCRF data from all clinical sites that conducted the study.

The Sponsor shall have the right to publish data from the study without approval from the individual investigators. Manuscript(s) and abstract(s) may only be prepared through cooperation between the Sponsor (or designee) and the study investigator(s). If an investigator wishes to publish information from the study, a copy of the manuscript must be provided to the Sponsor for review in accordance with the provisions of such investigator's written agreement with the Sponsor (or designee) before submission for publication or presentation. If requested by the Sponsor in writing, the investigator will withhold such publication in accordance with the provisions of such agreement.

22. APPENDICES

Appendix 1. Schedule of Events

Appendix 2. Sponsor's Signatures

Appendix 3. Investigator's Signature

APPENDIX 1. SCHEDULE OF EVENTS

| Schedule of Events Visit | S1 | S2 ¹ | T1 | T2 | T4 |
|---|------------|-----------------|-------|----------|-----------------------|
| Week | -6 | -1 | 0 | 3 | 6/EOS/ET ² |
| | Day | Day | | Day | Day |
| Procedure | -42 to -37 | -10 to -7 | Day 1 | 22 ± 3 | 43 ± 3 |
| Informed Consent | X | | | | |
| Enrollment Criteria | X | X | X | | |
| Demographics | X | | | | |
| Medical History | X | | | | |
| Concomitant\Prohibited Medications | X | X | X | X | X |
| Adverse Event Recording | | X | X | X | X |
| Physical Exam | | | X | | X |
| Weight ³ | X | | X | | X |
| Height/BMI | X | | | | |
| Vital Signs ⁴ | X | X | X | X | X |
| Serology ⁵ | | X | | | |
| Serum Pregnancy/FSH ⁶ | X | | | | |
| Urine Pregnancy ⁶ | | | X | | |
| TSH | X | | | | |
| Clinical Safety Labs ⁷ | X | | X | X | X |
| Basic Fasting Lipids ⁸ | X | X | X | X | X |
| Special Fasting Lipids and Other Biomarkers ⁹ | | | X | | X |
| Dietary and Lifestyle Counselling | X | X | X | X | |
| Randomization | | | X | | |
| Double Blind IMP Dispensing | | | X | X | |
| IMP Return | | | | X | X |

BMI = body mass index; FSH = follicle-stimulating hormone, TSH = thyroid-stimulating hormone, EOS = End of Study, ET = Early Termination.

¹ An optional visit approximately 1 week later MAY be completed if patient fails to meet a lipid entry criterion. If this optional visit is completed, the mean of the LDL-C values, or TG values, will be used to determine eligibility.

² All procedures will be completed at end of study or early termination.

³ Body weight will be measured in the morning while fasting, using consistent scales, after voiding, and without shoes and outerwear (eg, coats).

⁴ Vital signs will include SBP, DBP, and heart rate, and will be collected prior to any blood sample collection. Patient will rest for 5 minutes prior to assessments.

⁵ Serology for Hep B antigen, Hep C antibody.

⁶ FSH completed in appropriate postmenopausal women only; pregnancy test completed in non-postmenopausal women only.

⁷ Clinical safety labs include hematology, blood chemistry, and urinalysis. Coagulation panel ONLY in patients receiving anticoagulants measured only at T1 and repeat 3-5 days after starting IMP.

⁸ Basic fasting lipids include total cholesterol, calculated LDL-C, HDL-C, non-HDL-C, and triglycerides.

⁹ Includes ApoB and hs-CRP

# **Revision History**

Ite m No.	Version Affecte d	Description of change						
1	1.0	Section 5.1 General Statistical Considerations: Changed Analysis visit window.  From						
		Visit	S1	S2	T1	T2	T3, EOS	
		Slotted Study Week	-6	-1	0	3	6	
		Target Study Day	-42	-7	1	22	43	
		Analysis Visit Windows	[-∞,-37]	[-10,-1]	[1,7]	[8,28]	[29,+∞]	
		Protocol defined visit window	-42 to -37	-10 to -7	1	22±3	43±3	
		То						
		Visit	S1	S2	T1	T2	T3, EOS	
		Slotted Study Week	-6	-1	0	3 22	6	
		Target Study Day Analysis Visit	-42 [-∞,-37]	-7 [-36,-1]	[1]	[2,28]	43 [29,+∞]	
		Windows						
		Protocol defined visit window	-42 to -37	-10 to -7	1	22±3	43±3	
2	1.0	Section 5.2.6 Medical History: Removed mITT population set.  General medical history will be summarized by treatment group, as well as overall, for safety population and mITT population and presented in a by-patient listing. Where appropriate, terms will be coded using the Medical Dictionary for Regulatory Activities (MedDRA) Version 19.1 or later.						
3	1.0	Section 5.3.1 & 5.3.2: Updated for non-parametric analysis.  An analysis of covariance (ANCOVA) with treatment group as factor and baseline LDL-C as a covariate will be performed to compare triplet therapy versus placebo for the primary endpoint using the mITT population. The least squares mean (LSM) and standard error (SE) will be provided for both treatment groups, along with the placebo-corrected LSM, its 95% confidence interval (CI), and associated p-value. Statistical testing of primary efficacy endpoint will be 2-sided and conducted at the 5% level of significance. To account for potential unequal variance between the treatment groups, the ANCOVA model will be implemented within mixed model framework and the repeated/group= option will be used to allow estimating the residual variances separately between the groups. Q-Q plot will be performed to assess normality of data by treatment. If the assumptions were severely violated, non-parametric rank based approach rank. ANCOVA bylefficacy endpoints will be considered.						

Confidential Page 3 of 18

# 1 List of Abbreviations

Abbreviation or Specialist Term	Explanation
AE	Adverse event
AESI	Adverse events of special interest
ALB	Albumin
ALK-P	Alkaline phosphatase
ALT	Alanine aminotransferase
ANCOVA	Analysis of covariance
ApoB	Apolipoprotein B
AST	Aspartate aminotransferase
BMI	Body mass index
BP	Blood pressure
BUN	Blood urea nitrogen
Ca	Calcium
CI	Confidence interval
CK	Creatine kinase
$CO_2$	Carbon dioxide
CPK	Creatine phosphokinase
CRF	Case Report Form
DBP	Diastolic blood pressure
eCRF	Electronic case report form
eGFR	Estimated glomerular filtration rate
EOS	End of Study
FSH	Follicle-stimulating hormone
HBsAg	Hepatitis B surface antigen
Hct	Hematocrit
HCV	Hepatitis C virus
HDL-C	High-density lipoprotein cholesterol
НеГН	Heterozygous familial hypercholesterolemia
hs-CRP	High-sensitivity C-reactive protein
ICH	International Conference on Harmonisation
IMP	Investigational medicinal product
IND	Investigational New Drug Application
INR	International normalized ratio
mITT	Modified Intention-to-treat
IWRS	Interactive web response system
LDH	Lactate dehydrogenase
LOCF	Last observation carried forward
LSM	Least square mean
MCH	Mean corpuscular hemoglobin
MCHC	Mean corpuscular hemoglobin concentration
MCV	Mean corpuscular volume
MedDRA	Medical Dictionary for Regulatory Activities

Confidential Page 5 of 18

Abbreviation or Specialist Term	Explanation
non-HDL-C	Non-high-density lipoprotein cholesterol
PE	Physical exam
PK	Pharmacokinetic(s)
PMM	Pattern mixture model
PT	Prothrombin time
MedDRA PT	MedDRA Preferred term
RBC	Red blood cell
SAE	Serious adverse event
SAP	Statistical Analysis Plan
SBP	Systolic blood pressure
SE	Standard error
SGOT	Serum glutamic oxaloacetic transaminase
SGPT	Serum glutamic pyruvic transaminase
SOC	System organ class
SOP	Standard operating procedures
SP	Safety population
TB	Total bilirubin
TC	Total cholesterol
TEAE	Treatment-emergent adverse event
TG	Triglycerides
TSH	Thyroid-stimulating hormone
ULN	Upper limit of normal
WBC	White blood cell
WHO	World Health Organization

Confidential Page 6 of 18

## 2 Introduction

The purpose of this document is to describe the statistical methods, data derivations and data summaries to be employed in ETC-1002-038. The preparation of this statistical analysis plan (SAP) has been based on International Conference on Harmonisation (ICH) E3 and E9 Guidelines and in reference to Protocol ETC-1002-038 (Protocol Final, November 11, 2016).

The SAP will supersede the protocol in the event of any differences between the two documents in the plans for data analysis, and the protocol will be amended if appropriate. The SAP will be included as an appendix in the clinical study report for this protocol.

# 3 Study Objectives and Endpoints

## 3.1 Objectives

The primary objective for this study is to assess the LDL-C lowering efficacy of triplet therapy with bempedoic acid 180 mg, ezetimibe 10 mg, and atorvastatin 20 mg versus placebo administered daily for 6 weeks in patients with elevated LDL-C.

The secondary objectives are:

- To assess the effect of triplet therapy versus placebo on non-high-density lipoprotein cholesterol (non-HDL-C), total cholesterol (TC), apolipoprotein B (ApoB), high-sensitivity C-reactive protein (hs-CRP), TG, and HDL-C
- $\bullet$  To assess the effect of triplet therapy versus placebo on percent of patients achieving LDL-C level <70 mg/dL
- $\bullet$  To assess the effect of triplet therapy versus placebo on percent of patients achieving LDL-C reduction >50%
- To assess the safety and tolerability of triplet therapy versus placebo

# 3.2 Primary Endpoints

The following endpoints will be used to evaluate the objectives of the study.

## 3.2.1 Primary Endpoint

• Percent change from baseline to Week 6 in LDL-C

## 3.2.2 Secondary Endpoints

- Percent change from baseline to Week 6 in non-HDL-C, TC, ApoB, hs-CRP, TG, and HDL-C
- Percent of patients with LDL-C <70 mg/dL at Week 6

Confidential Page 7 of 18

• Percent of patients with LDL-C reduction ≥50% from baseline to Week 6

#### 3.2.3 Safety Endpoints

- Patient incidence of adverse events
- Clinical safety laboratory (including hematology, blood chemistry, and urinalysis) results
- Vital signs and physical examination (PE) findings

# 4 Study Design

# 4.1 Study Design

This is a Phase 2, multicenter, randomized, double-blind, placebo-controlled, parallel group study. Patients will initially undergo screening at Week -6 (Visit S1). Eligible patients will begin washout of all LDL-C-lowering drugs and nutritional supplements at least 5 weeks prior to randomization. Patients will return at Week -1 (S2) for lipid and/or other assessments. Patients who are deemed not eligible for randomization at any point during screening will be notified by clinical site personnel and considered screen failures. At Week 0 (Visit T1), approximately 60 patients will be randomized in a ratio of 2:1 to receive either triplet therapy (bempedoic acid 180 mg + ezetimibe 10 mg + atorvastatin 20 mg) or placebo once daily for 6 weeks. Randomized patients will return for clinic visits at Week 3 (Visit T2) and Week 6 (Visit T3). Total treatment duration will be 12 weeks (6 weeks screening and 6 weeks treatment) with the option to extend screening by 1 additional week. Up to approximately 20 centers in the US will participate in this. Additional sites may be invited to participate to ensure study timelines are met.

For details of study assessments, see the Schedule of Events in Appendix 1.

#### 4.2 Randomization

The randomization number will be determined by a computer-generated random code and will correspond to a treatment group according to patient's sequential entrance into the study. The randomization schedule for blinding of treatment assignment will be generated by the contract research organization (CRO), provided to IWRS, and released only after the study is complete and the database is locked. A patient is considered to be randomized when they have been assigned a randomization number by IWRS.

# 4.3 Sample Size Justification

Confidential Page 8 of 18

# 5 Statistical and Analytical Plans

#### 5.1 General Statistical Considerations

In general, summary statistics for continuous variables will include the number of patients, mean, median, standard deviation or standard error, first and third quartiles, minimum, and maximum. Minimum and maximum will be presented same number of decimal places as reported/collected, one additional decimal place for mean and median, and two additional decimal places for SD.

For categorical variables, the frequency and percentage will be given. Percentage will be presented with one decimal place. All categories will be presented (even if no patients are counted in the category). Counts of zero in any category will be presented without percentage.

Data will be presented on listings in order of patient/patient, assessment date and assessment (in order collected on CRF, unless specified otherwise). Dates will be presented in format DDMMMYYYY.

The visit schedules and window are shown below.

Visit	S1	S2	T1	T2	T3, EOS
Slotted Study Week	-6	-1	0	3	6
Target Study Day	-42	-7	1	22	43
Analysis Visit Windows	[-∞,-37]	[-36,-1]	[1]	[2,28]	[29,+∞]
Protocol defined visit window	-42 to -37	-10 to -7	1	22±3	43±3

# 5.2 Statistical Analysis Plans

#### 5.2.1 Analysis Sets

### **5.2.1.1** Safety Population (SP)

The Safety Population (SP), used for all of the safety summaries, is defined as all randomized patients who received at least 1 dose of study medication. Patients in the SP will be included in the treatment group that they actually received, regardless of their randomized treatment.

#### 5.2.1.2 Modified Intent-to-Treat Population (mITT)

The modified Intent-to-Treat (mITT) population, used for all of the efficacy analyses, is defined as all randomized patients who received at least 1 dose of Investigational medicinal product (IMP) and have a baseline assessment and at least 1 post-baseline assessment, excluding any assessment taken more than 2 days after a dose of IMP.

Confidential Page 9 of 18

Patients in the mITT will be included in their randomized treatment group, regardless of their actually received treatment.

#### **5.2.2** Baseline Definition

Baseline for LDL-C, non-HDL-C, HDL-C, TC, and TG is defined as the mean of the values from Week -1 (Visit S2) and predose Day 1/Week 0 (Visit T1), while baseline for ApoB and hs-CRP is defined as the predose Day 1/Week 0 (Visit T1) value. If only one value is available either at Week -1 or Week 0, then that value will be used as baseline.

Baseline of other laboratory evaluations and vital signs is defined as the last value prior to the first dose of study medication, except baseline of blood pressure is defined as mean of 2 measures at same visit.

#### **5.2.3** Protocol Violations and Deviations

A full list of protocol violations and deviations will be compiled and reviewed by the clinical team to identify major versus minor violations/deviations before final database lock. For violations at study entry, patients will be assessed against the inclusion and exclusion criteria of the protocol. For on-study deviations, compliance with the protocol will be examined using blinded review of the database with regard to prohibited therapies, and timing and availability of planned assessments. The determination of major versus minor protocol deviations will be conducted prior to the database lock. Any protocol deviation related to inclusion/exclusion criteria will be summarized in table as well as listing. Any major on-study protocol deviation will also be summarized by treatment group.

#### 5.2.4 Patient Disposition

Disposition, including reason for withdrawal from IMP and the study, will be summarized by treatment group. In addition, the number of patients who withdraw from the study and withdraw from study drug will be summarized by discontinuation reason.

#### 5.2.5 Demographic and Baseline Characteristics

Demographic information and important patient baseline characteristics including, but not limited to, gender, race, age, and baseline lipid parameter values will also be summarized by treatment group.

The following demographic and baseline characteristics will be summarized by treatment group, as well as overall, for safety population and for mITT population: age (years), gender, race, ethnicity, height (cm), weight (kg), body mass index (kg/m2), systolic and diastolic blood pressure (mmHg), fasting lipid parameters (TC [mg/dL], calculated LDL-C [mg/dL], HDL-C [mg/dL], non-HDL-C [mg/dL] and TG [mg/dL]), apoB (mg/dL), and hs-CRP (mg/dL).

Confidential Page 10 of 18

Data will be summarized using descriptive statistics for continuous variables and using counts and percentages for categorical variables by treatment group and overall. Age will be summarized as a continuous variable and by age group (18-40, 41-64, 65-74, and >=75).

### 5.2.6 Medical History

General medical history will be summarized by treatment group, as well as overall, for safety population and presented in a by-patient listing. Where appropriate, terms will be coded using the Medical Dictionary for Regulatory Activities (MedDRA) Version 19.1 or later.

#### 5.2.7 Prior Medications and Concomitant Medications/Procedures

Prior medications are defined as medications that ended prior to the initiation of double-blind study drug. Concomitant medications are defined as medications that were ongoing at the time of double-blind study drug initiation or new medications that started post double-blind study drug initiation and within 30 days following the date of the last dose of study drug.

Medications, including prior statin medications, will be coded using WHO Drug (Sept 2016, or later). The frequency of use of prior medications and use of concomitant medications will be summarized by treatment group, as well as overall, for the safety population according to Anatomical Therapeutic Chemical (ATC) class and preferred term. Prior medications, concomitant medications, and concomitant procedures will be listed for each patient.

#### 5.2.8 Study Drug Exposure and Compliance

The length of exposure to study drug (triplet therapy or placebo) will be calculated as the number of days from the first dose of double-blind study drug to the last dose of double-blind study drug, regardless if the patient missed one or more doses of study drug. If last dose of study treatment is missing, then the last IMP return date will be used for imputation of end of treatment date. Length of exposure will be summarized by treatment group using descriptive statistics for the safety population.

The number and percentage of patients who were compliant with taking study drug will be summarized by treatment group and post-baseline time point for the safety population for the following categories 0 - <50%; >= 50 - <80%; >= 80%. Compliance at each Visit (x) will be assessed by counting the number of tablets that are returned as unused study drug and querying the patient regarding daily intake and calculated using the formula: 100\* (Number Dispensed at Visit x-1 – Number Returned at Visit x) / (Duration in days between Visit x and Visit x-1). Compliance at each visit and overall compliance during the study will be calculated by programmer.

The study drug administration and compliance data, including reasons for poor compliance, will be listed for each patient.

Confidential Page 11 of 18

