8. TREATMENT OF PATIENTS

8.1. Administration of Investigational Medicinal Product

During the Treatment Period, patients will be randomized to receive IMP of either bempedoic acid 180 mg + ezetimibe 10 mg + atorvastatin 20 mg or placebo once daily. Each daily allotment of IMP is comprised of one bempedoic acid tablet, one overencapsulated ezetimibe tablet and one overencapsulated atorvastatin tablet provided in a blister package. The placebo blister pack will contain the corresponding matching placebo of the three drugs. Patients will be instructed to ingest IMP orally once daily with or without food. On clinic visit days, patients will be instructed to delay ingestion of IMP until all study procedures have been completed.

If the patient forgets to take IMP on nonclinic visit days, it may be taken up to 12 hours later the same day. After that time, the patient should not take IMP that day and should resume ingestion of IMP the following morning. Details describing the reasons for missed doses should be documented in the patient's medical records and electronic case report form (eCRF). Extra IMP is provided and can be used, if needed, prior to the next visit or to replace an allotment of IMP that cannot be used because it is lost or damaged.

Other details regarding IMP, including description, supply and control, accountability, handling, and disposal are provided in Section 9.

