9.5. Investigational Medicinal Product Accountability

Patients will be instructed to return all packaging and unused IMP at every visit for assessment of adherence and drug accountability.

Accurate records of the receipt of all IMP shipped by the Sponsor (or designee) and the disposition of that IMP must be maintained.

IMP records or logs must comply with applicable regulations, local law, and guidelines, and should include:

- Amount received/placed in storage area
- Amount currently in storage area
- MED ID number for all IMP
- Dates and initials of person(s) responsible for IMP inventory (including entry/movement/disposition)

- Date and amount of IMP dispensed to each patient, including unique patient identifiers
- Date that IMP was returned by patient, assessment of adherence, and relevant documentation of discrepancies
- Nonstudy disposition (eg, lost, broken, wasted)
- Amount returned to Sponsor (or designee)/destroyed or amount destroyed per local standard operating procedure (SOP) following accountability by site monitor.

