12.1.5.3.2. Monitoring and Management of Elevated Creatine Kinase

If at any time after randomization a patient experiences a marked CK elevation $>5 \times ULN$, the patient will undergo repeat confirmatory assessment as soon as is reasonably possible, preferably within 3 to 7 days of the laboratory result becoming available. If initial CK elevation is $>10 \times ULN$, patients will be instructed to discontinue IMP immediately (instead of continuing IMP until repeat lab value is assessed). It is very important that repeat confirmatory assessment occur as soon as possible (within a day of stopping IMP).

Repeat CK assessment will include query for the nature, duration and intensity of any muscle symptoms; review possible predisposing factors, such as unaccustomed exercise, heavy alcohol intake, viral illness (consider performing serology), concomitant medications, and/or other conditions which can cause myopathy; physical examination for muscle tenderness, weakness, and rash; measure serum creatinine, dipstick urinalysis ± microscopy if indicated; and basic metabolic panel.

• If the repeat CK assessment confirms an unexplained (ie, not associated with recent trauma or physically strenuous activity) CK abnormality >5 × ULN, if asymptomatic the investigator with input from the Sponsor may consider continuing IMP with continued CK assessments every 1-2 weeks.

- If the repeat CK assessment confirms an unexplained (ie, not associated with recent trauma or physically strenuous activity) CK abnormality as listed below, the patient should discontinue IMP:
 - >5 × ULN that is associated with symptoms of muscle pain, muscle weakness, or dark urine; or
 - >10 × ULN, even in the absence of symptoms.
- At the investigator's discretion, IMP may be interrupted and the patient rechallenged with IMP after CK has returned to the baseline level.

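### The SAP compliance formula counts unreturned lost doses as taken and instructed off-drug days as missed, so some patients fall in the wrong compliance category

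*SAP*

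**What the plan says.** SAP 5.2.8 sets visit compliance at 100 times "Number Dispensed at Visit x-1 – Number Returned at Visit x) / (Duration in days between Visit x and Visit x-1" and tabulates patients by arm and time point in the safety population, using the "following categories 0 - <50%; >= 50 - <80%; >= 80" per cent. The top class has no upper bound. The same section mentions "querying the patient regarding daily intake" and a listing of reasons for poor compliance, but gives no rule by which either alters the calculated value.

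The protocol foresees both situations that the formula leaves out.

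- **Lost doses.** Section 8.1 supplies extra IMP, among other uses "to replace an allotment of IMP that cannot be used because it is lost or damaged". Section 9.5 makes sites record "Nonstudy disposition (eg, lost, broken, wasted" and also states: "Patients will be instructed to return all packaging and unused IMP at every visit".
- **Stops between visits.** Under 12.1.5.3.2, for the highest initial CK results, "patients will be instructed to discontinue IMP immediately". Sections 12.1.5.3.1 (liver tests), 12.1.5.3.3 (LDL-C), 12.1.5.3.4 (TG) and 13.2.4 (pregnancy) also direct or allow IMP to be stopped. The liver and CK sections allow interruption followed by rechallenge.

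**The concern.** Dispensed minus returned equals doses taken only if every untaken dose comes back. A lost dose does not, so the formula treats it as swallowed. The visit-to-visit interval equals the doses due only if the patient was meant to dose on every day of it. After an instructed stop that is no longer so, and the off-drug days are scored as missed.

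The first error hides under-dosing; the second makes an obedient patient look non-adherent. SAP 5.2.8 measures length of exposure from first to last dose and ignores gaps, so the compliance table is where a reader would look for doses missed within the treatment period. With about 60 patients randomised 2:1 (about 40 and 20), one misclassified patient moves an arm's percentage by 1/40 = 2.5 points or 1/20 = 5 points.

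**Working it through.** The plan states no compliance percentage, so there is no figure to reproduce. The check applies the SAP formula to simple cases and compares the result with doses taken divided by days on which dosing was directed.

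**Inputs**

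- Doses per kit: 3 blister packs × 9 days = 27 (Protocol 9.3). One kit per dispensing visit is an assumption. It limits only how many doses can be lost and how high the score can go; otherwise the formula depends only on doses taken plus doses lost.
- Interval: 22 − 1 = 21 days for T1 to T2, and 43 − 22 = 21 days for T2 to T3 (Protocol 10.5.4 and 10.5.5). With the ±3-day windows, the ranges are 18 to 24 and 15 to 27 days.
- Unit: whole daily allotments.

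**Numerator: unreturned lost doses, 21 days**

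| Taken | Lost | Returned | Formula | True |
|---|---|---|---|---|
| 16 | 1 | 10 | (27 − 10)/21 = 81.0% | 16/21 = 76.2% |
| 10 | 1 | 16 | (27 − 16)/21 = 52.4% | 10/21 = 47.6% |
| 8 | 9 (one blister) | 10 | (27 − 10)/21 = 81.0% | 8/21 = 38.1% |

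The first two patients each rise one category; the third goes from the lowest to the highest. One lost dose is also enough at the other interval lengths:

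- 15 days, 11 taken: 73.3% becomes 80.0%.
- 18 days, 14 taken: 77.8% becomes 83.3%.
- 24 days, 19 taken: 79.2% becomes 83.3%.
- 27 days, 21 taken: 77.8% becomes 81.5%.

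If nothing is returned, the score is 27/21 = 128.6%, unmarked within the top class.

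**Damaged but returned.** 16 taken, 1 damaged and returned, 10 unused returned: (27 − 11)/21 = 76.2%, which is correct.

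**Denominator: instructed off-drug days, 21 days, every directed dose taken**

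| Case | Formula | Against directed days |
|---|---|---|
| Stop after 16 doses (5 days off) | 16/21 = 76.2% | 16/16 = 100% |
| Stop after 10 doses (11 days off) | 10/21 = 47.6% | 10/10 = 100% |
| 7-day interruption, then rechallenge | 14/21 = 66.7% | 14/14 = 100% |

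Four days off leave the patient in the top class (17/21 = 81.0%); five do not. If the early termination visit takes place at the stop, the interval ends there and there is no error.

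**Whole treatment period.** The SAP gives no formula for overall compliance. If the same one is applied over 42 days, a stop after 33 doses gives 33/42 = 78.6% and after 20 doses 20/42 = 47.6%. One lost dose moves 33 taken from 78.6% to 34/42 = 81.0%.

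**The case against.** The strongest reply is that little depends on this table. Neither the safety population nor the mITT population is defined by compliance, poor adherers stay in the study (Protocol 9.4), and no test or covariate uses the categories. Length of exposure shows permanent stops, SAP 5.2.4 summarises reasons for leaving study drug, and reasons for poor compliance are listed by patient. One can also argue that dividing by the visit interval deliberately measures drug received against plan. All of this limits the consequence. It does not make the figure right: the table is labelled as compliance, and unreturned lost doses inflate it on either view of the denominator.

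Four stronger readings are tempting, and the documents do not support them.

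- *Every lost or damaged dose is scored as taken.* Unused IMP is to be returned, and a damaged dose that comes back is counted correctly. A loss made good from the spare supply also need not change the category: 21 taken and 1 lost gives 22/21 = 104.8%, still in the top class.
- *Every safety stop is scored as poor adherence.* Week 6 is also the early termination visit, and Protocol 10.6 calls for withdrawing patients whose treatment is interrupted on health grounds. Where the final visit follows at once, the error vanishes. It remains possible because 12.1.5.3.1 and 12.1.5.3.2 allow rechallenge, SAP 5.2.4 separates leaving drug from leaving the study, and pregnant patients stop drug but stay under follow-up.
- *The table will show a false difference in adherence between arms.* That would need an imbalance in stops or losses, and the documents give no expected frequency of either.
- *The LDL-C result is at risk.* No efficacy analysis uses compliance.

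**Conclusion.** The point holds in limited form. Followed as written, the formula misstates compliance for two kinds of patient whom the protocol itself anticipates, and the category can be wrong in either direction. One unreturned lost dose is enough to raise it for a patient just below a cut-off; five instructed off-drug days in a 21-day interval are enough to lower it for a patient who took every directed dose.

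The result assumes that whole daily allotments are counted and that no correction is made from the patient query, since the SAP gives no rule for one. The downward error also needs off-drug days before the next visit. How many patients would be affected cannot be judged from the documents. The consequence is confined to a descriptive safety-population table, so this is a minor correction.

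**What to change.** In SAP 5.2.8:

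1. Define doses taken as dispensed, minus returned, minus logged lost, broken or wasted doses that were **not returned**. The restriction matters. With 27 dispensed, 20 taken, 1 broken and returned, and 6 unused returned, the present formula correctly gives 27 − 7 = 20; subtracting the broken dose again would give 19.
2. Define the denominator as the visit interval minus days off drug on protocol or investigator instruction. This covers permanent stops and interruptions alike. Merely ending the interval at the stop date would fail for a rechallenged patient: 7 doses, 7 days off and 7 more doses would give 14/7 = 200% instead of 14/14 = 100%.
3. Report instructed stops and interruptions, with dates, beside the compliance table.
4. List values above 100% individually instead of leaving them unmarked in the top class.

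Recalculated this way, the lost-dose patients return to 76.2%, 47.6% and 38.1%, and each patient who took every directed dose scores 100%.

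The cost is SAP wording and minor programming, with one burden: if lost-dose counts and interruption dates are held only on site logs, they must be carried into the analysis data. The sponsor should also reconcile Protocol 10.6 (withdrawal, with no changed regimen) with 12.1.5.3.1 and 12.1.5.3.2 (interruption and rechallenge), because which applies determines when off-drug days can fall between visits.
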